**Approved May 1st, 2018**

## **I. Background**

Human Immunodeficiency Virus (HIV) infected patients treated with anti retroviral drugs may experiencing immunological failure known as immunological non responders (INR). In this particular group of patient, the level of CD4 still below normal limit even though the HIV virus is suppressed (undetected). Immunological non responders (INR) were associated with high morbidity. Hypothetically, INR patients have decreased gut integrity and immunity due to increased gut inflammation and further causing microbial translocation. Probiotics may improved gut inflammation condition, however the direct benefits of probiotics supplementation for INR HIV patients have not been studied. Growing number of INR HIV patients will be associated with higher economical burden and decreased quality of life.

Microbial translocation was thought as the underlying mechanism of persistently immune activation which may lead to immunological failure condition in virally suppressed HIV patients. Decreased number of T- helper 17 (Th17) in HIV patients may facilitated microbial translocation. HIV Virus destroyed the CD4 T memory cells which mainly found in *gut associated lymphoid tissue* (GALT), thus resulting in lower production of Th17 in gut mucosal tissue. One of the microbial translocation marker is 16S ribosomal DNA (16S rDNA) bacteria blood level. Gut inflammation may be represented by fecal calprotectin level.

Probiotics supplementation in HIV patients was proposed may increase gut integrity and immunity through several mechanisms: improving tight junction gut mucosal, increasing mucin production, regulating Th17; therefore decreasing gut inflammation and microbial translocation. Improved gut inflammation and decreased microbial translocation may increased the immune recovery in INR HIV patients

This clinical trial is intended to evaluate the immune recovery effect of Probiotics supplementation in INR HIV patients.

## **II. Objectives**

### **A. General Objectives**

To determine the effect of Probiotic in immune response for immunological non responder HIV patients

### **B. Specific Objectives**

#### **a. Primary Objectives**

- i. To determine the average CD4 value in immunological non responder HIV patients treated with Probiotic compared to placebo
- ii. To determine the average T helper 17 value in immunological non responder HIV patients treated with Probiotic compared to placebo
- iii. To determine the average 16S rDNA value in immunological non responder HIV patients treated with Probiotic compared to placebo
- iv. To determine the fecal calprotectin value in immunological non responder HIV patients treated with Probiotic compared to placebo

#### **b. Secondary Objectives**

To determine the effect of Probiotic supplementation towards quality of life improvement in immunological immunological non responder HIV patients, using HIV symptom index.

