### C. Study Population

1. Targeted Population: HIV patients with Immunological Non-responder condition in Indonesia
2. Sample: HIV patients with Immunological Non-responder condition in Indonesia
3. Inclusion Criteria:
  - a. HIV positive patients aged 18-55 years old
  - b. had already treated with first line Highly Active Anti Retroviral Therapy for at least 6 months
  - c. had CD4 level of 200-410 cell/ $\mu$ L
  - d. undetectable Viral Load (<34 copies/ml blood)
  - e. agreed to participate in the study and signed the informed consent
4. Exclusion Criteria:
  - a. Pregnant patients
  - b. Lactating patients
  - c. Known *Lactobacillus* allergy
  - d. Body Mass Index (BMI) <16 kg/m^2
  - e. Under Tuberculosis treatment or other acute illness, acute diarrhea,
  - f. routinely taking selenium containing vitamin in last 1 month,
  - g. routinely consuming probiotics containing product in last 1 month
5. Estimation Sample Size: 80 samples. Which will be divided into two groups equally.
6. Study Procedure

[figure not shown]
Eligible patients will be approached to be enrolled in the clinical trial. Informed consent will be obtained. Patients will be randomized and divided into two groups, intervention and placebo group. Intervention group will receive Probiotics (Chewable tablet) containing *Lactobacillus plantarum*, *Streptococcus thermophiles*, *Bifidobacterium bifidum* once daily. While, Placebo group will receive placebo which had identical shape, flavor, and smell as the interventional drug.

Intervention will be held for 12 weeks. CD4, Th17, 16S Ribosomal RNA, and fecal calprotectin level will be checked at the 0 week and repeated after 12 weeks of intervention. Self administered HIV Symptoms Index questionnaire will be filled by the respondent on 0,4,8,12 weeks of intervention. Food frequency questionnaire will be filled by the respondents with the help of nutritionist on 0,4,8,12 weeks of intervention.

7. Side effects

All side effects that may arise and related to probiotics intake will be assessed and reported. Appropriate medical advice will be provided.

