#### IV. Statistical Analysis Plan

All Data will be analyzed using SPSS 24.0 (SPSS) for Windows. Laboratory parameters will be compared between two different times and also compared between two groups by using paired and independent t test (if normally distributed) or using Wilcoxon and Mann Whitney (if not normally distributed). Statistically significance was determined by p value <0.05. Intention to Treat analysis will be used. HIV symptom index and food frequency will be reported descriptively.

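### The only secondary objective is worded as quality of life, but a symptom index reported descriptively supports only a statement about self-reported symptoms

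*Combined protocol and SAP*

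**What the plan says.** Section II.B.b contains one secondary objective: "To determine the effect of Probiotic supplementation towards quality of life improvement in immunological immunological non responder HIV patients, using HIV symptom index". The target is quality of life and the named tool is a symptom index.

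Section III.C.6 (Study Procedure) gives the collection schedule: "Self administered HIV Symptoms Index questionnaire will be filled by the respondent on 0,4,8,12 weeks of intervention". The only other questionnaire there is dietary: "Food frequency questionnaire will be filled by the respondents with the help of nutritionist on 0,4,8,12 weeks of intervention".

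Section IV (Statistical Analysis Plan) treats the two kinds of data differently. For the laboratory measures, "Laboratory parameters will be compared between two different times and also compared between two groups", with the tests named and a significance rule attached ("Statistically significance was determined by p value <0.05"). For the questionnaires, the whole plan is "HIV symptom index and food frequency will be reported descriptively".

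**The concern.** Two gaps sit on top of each other. The first is between construct and instrument: the objective is about quality of life, and what is collected is an index of symptoms. The second is between objective and analysis: the objective is to determine an effect, which needs a comparison of the arms, and the analysis section plans no such comparison for this outcome.

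All four primary objectives are laboratory values, so this is the trial's only objective about how patients feel. A result reported under its present heading would be read as evidence on quality of life. The plan gives no basis for taking the index that far in either direction, whether the scores change or stay flat.

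**Working it through.** This is a check of consistency between sections. The plan gives no figure on this point to reproduce.

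**Step 1. What is to be learned.** Section II.B.b: an effect of the probiotic on quality of life.

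**Step 2. What is measured.** Section III.C.6: laboratory values at weeks 0 and 12, and two questionnaires (symptoms and diet) at weeks 0, 4, 8 and 12. The readable text names no quality-of-life instrument.

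**Step 3. Whether anything links the two.** Quality of life appears in one other place, the Background (section I), as part of the rationale, without a definition or domains. The document does not describe the items, scoring or direction of the index, or how a score would be translated into quality of life. No citation is attached to the index where it is named, and none of the nine titles in section V concerns it. The only link is that the objective names the index as its tool.

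**Step 4. What is analysed.** Section IV: paired and two-sample tests for laboratory parameters, and description only for the index. It does not say whether the description is by arm, which score is used, or which visit matters most.

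**Step 5. What conclusion follows.** Steps 2 and 4 together yield a description of self-reported symptoms over 12 weeks. Going from there to quality of life needs the link missing at step 3. Going from there to an effect needs the comparison missing at step 4.

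**Context for the optional comparison.** This matters only if the sponsor keeps an effect objective.
- Input: "Estimation Sample Size: 80 samples. Which will be divided into two groups equally" (section III.C.5), so n = 80 / 2 = 40 per arm.
- Assumptions: two-sided α = 0.05 (the plan does not state sidedness), a normal approximation, and every patient contributing a week-12 score.
- Detectable standardised difference: d = (z₀.₉₇₅ + z_power) × √(2/n), with √(2/40) = 0.2236.
  - 80% power: (1.960 + 0.842) × 0.2236 = 0.63 SD.
  - 90% power: (1.960 + 1.282) × 0.2236 = 0.72 SD.
- Power for assumed true differences: Φ(d / 0.2236 − 1.960).

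| Assumed difference (SD) | Power |
|---|---|
| 0.2 | 14% |
| 0.5 | 61% |
| 0.8 | 95% |

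A week-12 comparison could therefore detect a large difference but would often miss a moderate one. None of this bears on whether a symptom index measures quality of life.

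**The case against.** The best defence has three parts. The objective names its instrument in the same sentence, so nobody is misled about what was recorded. Symptoms are related to quality of life, so using symptom burden as an indicator is a permissible design choice. And because section IV plans only description, no inferential claim about quality of life is in prospect.

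Much of this stands, and it is why the point is minor. It does not remove the mismatch. Naming a tool does not establish that it measures the stated construct, and the document makes no argument that it does. A relation between symptoms and quality of life supports a conclusion about symptoms. Descriptive analysis sits badly with an objective to determine an effect, so the third argument exposes the second gap instead of closing it.

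A reader might infer several stronger things that the document does not support:
- **Higher scores are worse, so improvement means a fall.** The scoring and its direction are not given.
- **The index contains nothing on functioning or wellbeing.** The items are not shown, so this cannot be checked.
- **Patients with suppressed virus will start with few symptoms and have no room to improve.** There are no baseline symptom data. Entry is based on CD4 and viral load, in line with the primary objectives, so the lack of a symptom threshold is not in itself a fault.
- **The plan commits to reporting a score change as a quality-of-life change.** There is no such reporting rule and no pre-written conclusion. The objective sets out to determine an effect and does not assert one.
- **Self-report is the weakness.** Quality of life is itself usually self-reported, and the trial is double-blind.

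**Conclusion.** The concern holds in a limited form. The only secondary objective names a broader construct than its only instrument is shown to measure, and its planned analysis is description without a comparison of arms. As written, the trial can describe self-reported symptoms. It cannot support a conclusion about an effect on quality of life.

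The size is one whole secondary objective, at minor severity. The primary objectives do not depend on it, and neither does any trial decision stated in the plan. There is no numerical measure of the error. Multiplying 80 patients by 4 visits gives 320 planned questionnaires, but that counts forms and says nothing about bias.

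The verdict assumes that the study-procedure figure, which is not visible in the text available, and the pages left out of it name no further patient-reported instrument.

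**What to change.** Reword section II.B.b along these lines: *to describe HIV-related symptom burden by treatment group at weeks 0, 4, 8 and 12, using the HIV Symptoms Index.* Make no quality-of-life claim from it. This agrees with the schedule in section III.C.6 and with the descriptive plan in section IV, which then needs only the words *by treatment group*.

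If the sponsor prefers to keep an objective of determining an effect, it should be an effect on symptom burden. Section IV should then state how the index is scored and add a comparison of the week-12 score between arms.

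The rewording needs no new patients, visits or questionnaires, and its downside is a narrower stated claim. The comparison adds one analysis of data already being collected, with the limited power shown above. A genuine quality-of-life conclusion would need a quality-of-life instrument. That is a larger change and is not required to make the plan consistent.

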## **III. Methods**

### **A. Study Design**

This study is double-blind randomized control trial design

### **B. Time and Place**

This study will be conducted in Cipto Mangunkusumo National Central General Hospital, especially in Human Infectious Disease polyclinic. Enrollment will start on May 2018, and recruited until minimum sample size was fulfilled

### C. Study Population

1. Targeted Population: HIV patients with Immunological Non-responder condition in Indonesia
2. Sample: HIV patients with Immunological Non-responder condition in Indonesia
3. Inclusion Criteria:
  - a. HIV positive patients aged 18-55 years old
  - b. had already treated with first line Highly Active Anti Retroviral Therapy for at least 6 months
  - c. had CD4 level of 200-410 cell/ $\mu$ L
  - d. undetectable Viral Load (<34 copies/ml blood)
  - e. agreed to participate in the study and signed the informed consent
4. Exclusion Criteria:
  - a. Pregnant patients
  - b. Lactating patients
  - c. Known *Lactobacillus* allergy
  - d. Body Mass Index (BMI) <16 kg/m^2
  - e. Under Tuberculosis treatment or other acute illness, acute diarrhea,
  - f. routinely taking selenium containing vitamin in last 1 month,
  - g. routinely consuming probiotics containing product in last 1 month
5. Estimation Sample Size: 80 samples. Which will be divided into two groups equally.
6. Study Procedure

[figure not shown]
Eligible patients will be approached to be enrolled in the clinical trial. Informed consent will be obtained. Patients will be randomized and divided into two groups, intervention and placebo group. Intervention group will receive Probiotics (Chewable tablet) containing *Lactobacillus plantarum*, *Streptococcus thermophiles*, *Bifidobacterium bifidum* once daily. While, Placebo group will receive placebo which had identical shape, flavor, and smell as the interventional drug.

Intervention will be held for 12 weeks. CD4, Th17, 16S Ribosomal RNA, and fecal calprotectin level will be checked at the 0 week and repeated after 12 weeks of intervention. Self administered HIV Symptoms Index questionnaire will be filled by the respondent on 0,4,8,12 weeks of intervention. Food frequency questionnaire will be filled by the respondents with the help of nutritionist on 0,4,8,12 weeks of intervention.

7. Side effects

All side effects that may arise and related to probiotics intake will be assessed and reported. Appropriate medical advice will be provided.

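### The entry criteria do not separate patients still recovering on ART from immunological non-responders, and neither the analysis nor the stated conclusion allows for it

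*Combined protocol and SAP*

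**What the plan says.** The Background (section I) describes immunological non-responders (INR) as patients in whom "the level of CD4 still below normal limit even though the HIV virus is suppressed (undetected", and presents this as immunological failure. It gives no number, time span or CD4 gain. All four primary objectives and the secondary objective (II.B) are stated for INR patients, and III.C.1-2 names both the target population and the sample as "HIV patients with Immunological Non-responder condition in Indonesia".

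Three inclusion criteria in III.C.3 put this into practice: the patient "had already treated with first line Highly Active Anti Retroviral Therapy for at least 6 months" (b), "had CD4 level of 200-410 cell"/µL (c), and "undetectable Viral Load (<34 copies/ml blood") (d). None refers to a CD4 before or early in ART, to a plateau or inadequate rise, to a repeat CD4, to the date of the qualifying values, or to how long the virus has been suppressed.

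III.C.6 states that "CD4, Th17, 16S Ribosomal RNA, and fecal calprotectin level will be checked at the 0 week and repeated after 12 weeks of intervention". It does not say that the week-0 CD4 is the qualifying one, and viral load is not on that list. Section IV plans paired tests between the two times and independent tests between the two groups, with rank tests as the alternative. It names no covariate, no stratification and no sensitivity analysis. It also does not say whether the between-group test uses the week-12 value or the change.

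**The concern.** Non-response is a failure over time, whereas criteria b-d test a state at entry. Take an illustrative patient who began ART at a CD4 of 60, reached 260 at month 6 and has just become undetectable. This patient has gained 200 cells/µL and meets b, c and d.

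Three things are at stake if such patients enter:

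- Their CD4 can go on rising in either arm. That spreads out the CD4 changes and moves the within-arm mean upward without any treatment effect.
- If the probiotic helps them less than it helps true non-responders, the between-arm difference shrinks.
- Whatever is found will be reported for INR patients, although entry did not establish that condition.

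**Working it through.** **Inputs from the documents.** "80 samples. Which will be divided into two groups equally" (III.C.5), so 40 per arm; laboratory values at weeks 0 and 12 (III.C.6); p < 0.05 (section IV), taken here as two-sided because the plan does not say.

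**Inputs that must be assumed.** f = share of entrants still recovering; r = their probiotic effect relative to true non-responders; m = their extra 12-week CD4 rise, in SDs of CD4 change. The documents give none of these, so ranges are shown.

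**Step 1: the plan's own figure.** The total of 80 cannot be reproduced, because no effect size, SD, power or dropout is given. Solving backwards with the normal approximation, the standardised difference detectable with 80% power is

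d = (1.960 + 0.842) × √(2/40) = 0.626.

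This is the reference case, with 80% power if f = 0.

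**Step 2: CD4 variance when recovering patients benefit equally (r = 1).** The entrants are a mixture of two groups, so the SD of change is multiplied by √(1 + f(1−f)m²). For f = 40% and m = 1.0 this is √(1 + 0.24) = 1.114.

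**Step 3: the placebo arm's paired CD4 test with no treatment effect.** The mean drift is f × m. The noncentrality is f × m × √40 / √(1 + f(1−f)m²). For f = 40% and m = 1.0 it is 0.4 × 6.325 / 1.114 = 2.27, which gives 62% rejection where 5% is nominal.

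| f | m | SD multiplier | Between-arm power (step 2) | Placebo paired test rejects (step 3) |
|---|---|---|---|---|
| 20% | 0.25 | 1.005 | 80% | 6% |
| 20% | 0.5 | 1.020 | 78% | 10% |
| 20% | 1.0 | 1.077 | 74% | 22% |
| 40% | 0.25 | 1.007 | 79% | 10% |
| 40% | 0.5 | 1.030 | 78% | 23% |
| 40% | 1.0 | 1.114 | 71% | 62% |

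Using the t distribution instead of the normal changes the last column by at most about 2 points (62% becomes 60%).

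**Step 4: how plausible is m?** If recovery runs at 50-150 cells/µL per year (assumed), the 12-week rise is 50 × 12/52 = 12 to 150 × 12/52 = 35 cells/µL. Then m = 0.25 corresponds to an SD of CD4 change of 48-140 cells/µL, and m = 1.0 to only 12-35. The bottom rows of each block are therefore the extreme case.

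**Step 5: dilution, if recovering patients benefit less.** The effect becomes d × (1 − f(1−r)).

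| f | Power, r = 0 | Power, r = 0.5 | Power, r = 1 |
|---|---|---|---|
| 10% | 71% | 76% | 80% |
| 20% | 61% | 71% | 80% |
| 30% | 50% | 66% | 80% |
| 40% | 39% | 61% | 80% |

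The column r = 1 shows that dilution disappears if recovering patients respond equally. Steps 2-4 concern CD4. The documents give no data on how recovery would affect Th17, 16S rDNA or fecal calprotectin.

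**The case against.** The strongest reply is that the protocol does not contradict itself. Its description of INR is a CD4 still below normal with suppressed virus, and criteria b-d implement that. Calling the patient who went from 60 to 260 a responder brings in a trajectory definition that the protocol never adopted. This stands: the criteria define INR loosely but do not conflict with the Background.

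A reader might infer that normally recovering patients do enter and do dilute all four primary comparisons. The documents do not support that. Their share is unknown. Dilution needs a smaller benefit in such patients, and the Background describes the probiotic mechanism for HIV patients generally. The Background also links failed recovery to gut inflammation and microbial translocation, which is a reason to consider a smaller effect but not evidence of one.

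A reader might also infer that eligibility rests on one outdated CD4. The text states neither number nor date, CD4 is measured at week 0, and the flow figure is not available. What can be said is that no repeat or time window is written.

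Measurement noise around the 410 limit is a separate matter. A patient whose true mean lies just above 410 is misclassified against the cut-off but is not thereby recovering, so noise does not show how many recovering patients enter.

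What the objection leaves untouched is that recovery in progress is not excluded at entry, is not handled in the analysis, and is not reflected in how the conclusion is framed.

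**Conclusion.** The concern holds as a weakness of definition and analysis. Patients still recovering on ART can enter a trial whose objectives are all stated for non-responders. Such patients are equally likely in each arm, so the between-arm test remains valid.

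The loss of CD4 power from added variance is modest: from 80% to between 71% and 80% for f = 20-40% and m = 0.25-1.0. The within-arm paired CD4 test is the more exposed, with 6-62% rejection in the placebo arm over the same range. Dilution is possible but conditional: power of 39-76% for f = 10-40% if recovering patients get none or half of the benefit, and no dilution if they benefit equally. All these figures rest on assumed f, r and m and on a reference power of 80% that the plan does not state.

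The limit on what can be concluded about INR patients needs none of these assumptions. It follows from the criteria as written.

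**What to change.** 1. At week 0, record ART duration (it must be ascertained for criterion b in any case) and, where the clinic record has them, earlier CD4 and viral-load values with dates.
2. Make the primary between-arm comparison a baseline-adjusted model: week-12 value on arm, baseline value and ART duration. Name the scale for skewed markers in advance. This recovers only the part of the recovery variance that these covariates explain, and it does not restore a diluted effect.
3. Report within-arm changes descriptively, and draw no efficacy conclusion from paired tests.
4. State the conclusion for virally suppressed patients on first-line ART for at least 6 months with CD4 200-410 cells/µL.
5. Where records allow, add a sensitivity analysis in patients whose records show no adequate CD4 rise. The investigators should define adequate before unblinding. It will cover only patients with usable records.

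The cost is one or two extra baseline variables, an edit to section IV, and a narrower stated conclusion.

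Rewriting eligibility is a trade-off for the investigators and is not required. For example, suppose two CD4 values in range 6 months apart were demanded. Assume a geometric mean CD4 of 350-450, log-SD 0.4, within-person CV 15-25%, and a rise of 25-75 cells/µL over the 6 months. A simulation then still admits about 46-78% of rising patients who qualified on the first value, against 63-80% of stable ones. Such a rule slows recruitment and separates the two groups poorly.

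### The allergy exclusion names one of the three organisms in the active tablet; consider naming all three

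*Combined protocol and SAP*

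**What the plan says.** Section III.C (Study Population) holds all the relevant text.

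- Item 4c, the allergy exclusion: "Known *Lactobacillus* allergy".
- Item 6, the product: "Intervention group will receive Probiotics (Chewable tablet) containing *Lactobacillus plantarum*, *Streptococcus thermophiles*, *Bifidobacterium bifidum* once daily". The second name is taken to mean *Streptococcus thermophilus*.
- Item 6, duration: "Intervention will be held for 12 weeks".
- Item 6, the comparator: "Placebo group will receive placebo which had identical shape, flavor, and smell as the interventional drug". No placebo composition and no excipients for either product are given in the visible text.
- Item 6, the order of steps: "Eligible patients will be approached to be enrolled in the clinical trial. Informed consent will be obtained". Randomization follows.
- Item 5, allocation of the 80 patients: "Which will be divided into two groups equally".

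Two other exclusions come near the subject. Item 4e reads "Under Tuberculosis treatment or other acute illness, acute diarrhea", and item 4g reads "routinely consuming probiotics containing product in last 1 month". Item 7 provides for assessing and reporting side effects of probiotic intake.

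**The concern.** Exclusion 4c evidently exists to keep patients with a known allergy to the product from receiving it. The protocol states no rationale, so this is an inference, but it is hard to see another purpose. The rule is written around one genus, while the product is described as containing organisms from three. Nothing in the document explains why the precaution stops at *Lactobacillus*.

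At stake is patient safety at the point of entry. Staff who apply the list as written would have no criterion on which to exclude a patient who reports a known allergy to *Streptococcus thermophilus* or *Bifidobacterium bifidum*. The point has no bearing on the trial's inferences.

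**Working it through.** The plan has no figure of its own to reproduce here. The check compares the eligibility list with the stated product.

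**1. Organisms against the allergy criterion**

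| Organism in the active tablet (III.C, item 6) | Covered by 4c? |
|---|---|
| *Lactobacillus plantarum* | Yes |
| *Streptococcus thermophilus* | No |
| *Bifidobacterium bifidum* | No |

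Covered: 1 of 3. Not covered: 3 − 1 = 2 of 3.

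**2. Does any other criterion close the gap?**

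There are 5 inclusion criteria (3a to 3e) and 7 exclusion criteria (4a to 4g), so 5 + 7 = 12 in all.

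| Criteria | Subject | Allergy to the other two organisms? |
|---|---|---|
| 3a–3e | Age, time on antiretrovirals, CD4, viral load, consent | No |
| 4a, 4b | Pregnancy, lactation | No |
| 4c | *Lactobacillus* allergy | No |
| 4d | Low BMI | No |
| 4e | Tuberculosis treatment, acute illness, diarrhea | No |
| 4f | Selenium supplements | No |
| 4g | Recent routine probiotic use | No |

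One of 12 concerns allergy (4c), and 0 of 12 concern allergy to the two unnamed organisms.

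The two nearest criteria do not substitute. A currently well patient with an allergy history has none of the conditions in 4e. Criterion 4g removes recent users of probiotics; a patient who knows of such an allergy would be expected to avoid these products and so would pass 4g.

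**3. The rest of the document**

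Item 7 operates only once the tablet has been taken. No other visible section mentions allergy or hypersensitivity.

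**4. Exposure, if such a patient were enrolled**

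Eligibility is not exposure: the patient must still consent, enrol and be randomized. Conditional on that:

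- Chance of the active tablet: (80 / 2) / 80 = 40/80 = 1/2.
- Planned active doses: 1 per day × 7 days × 12 weeks = 84, fewer if treatment stops after a reaction.

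These figures would describe any randomized patient. They bound the exposure of one such patient and do not measure expected harm. An expected number of affected patients would need a prevalence, which the documents do not give, so none is computed.

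**The case against.** The textual mismatch is not in dispute; the case on the other side is that it hardly matters.

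- **No consequence is shown from the documents.** Nothing in them says that allergy to the two unnamed organisms is recognised, how common it is, or what reaction would follow. This stands, and it limits the point to a low priority. The documents give no rate for *Lactobacillus* allergy either, yet the sponsor chose to exclude it. Rarity lowers the importance of the gap but does not complete the list.
- **The size is a judgement.** Calling the number affected close to zero, or the extra screen failures very rare, is an opinion about prevalence that the documents do not support. That is correct, and both should be read as opinion. No calculation above uses them.
- **Relevant material is not visible.** The consent pages and the study-procedure figure were not available, and the Research Flow heading (III.D) has no visible content. A product-allergy warning could sit in any of these. This stands as a limit: the conclusion concerns the written criteria only and does not say that an allergic patient would reach dosing unnoticed.
- **The genus name may be shorthand for the whole product.** If so, the rewording only states what was meant. Read literally, 4c names one genus while item 6 names the three organisms separately.
- **Excipient wording goes beyond the evidence.** This is fair, since the visible text describes no excipients. That part of the change is optional.

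**Conclusion.** The concern holds. As written, the allergy exclusion covers 1 of the 3 organisms stated for the active tablet, and none of the 12 visible criteria covers the other 2. A patient with a known allergy to either of those is eligible under the list.

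Confidence is high for the mismatch in wording. The size of any safety consequence cannot be established from the documents. The conclusion rests on reading 4c literally and on the visible text alone. It is an improvement to consider, with no effect on sample size, error rate, endpoints or analysis.

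**What to change.** Reword exclusion 4c along these lines: *known allergy to Lactobacillus, Streptococcus thermophilus or Bifidobacterium*. Add the matching question to the screening form. Naming the two missing organisms is the correction. Extending the wording to *any other component of the study tablet or placebo* is a reasonable optional precaution.

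The cost is one line of protocol text and one screening question. The only downside is an occasional extra screen failure, expected to be very rare.

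### Section III.C.7 ties side-effect assessment and reporting to a judged relation to probiotic intake, and section IV plans no side-effect summary by arm

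*Combined protocol and SAP*

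**What the plan says.** Section III.C.7 (Side effects) is the only text on side effects in the protocol and SAP as supplied. Its operative sentence is "All side effects that may arise and related to probiotics intake will be assessed and reported". One further sentence promises medical advice. The item does not say who judges the relation to the product, when patients are asked, or whether events judged unrelated are kept.

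The design is a double-blind randomised comparison (III.A). On the comparator, III.C.6 says "Placebo group will receive placebo which had identical shape, flavor, and smell as the interventional drug". The planned 80 patients are allocated 1:1 (III.C.5: "Which will be divided into two groups equally").

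Section IV (Statistical Analysis Plan) sets out two kinds of output. For laboratory values, "Laboratory parameters will be compared between two different times and also compared between two groups". For the questionnaires, "HIV symptom index and food frequency will be reported descriptively". Side effects do not appear in that section. The objectives in section II include none on safety.

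**The concern.** Randomisation, blinding and a matched placebo let harm be judged by comparing event counts between arms. That comparison needs no opinion on the cause of any single event. It does need every event to be counted in the same way in both arms.

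III.C.7 puts an opinion on cause ahead of the count. If an event is assessed and reported only when thought related to the product, one attributed to something else may never reach the data. Section I hypothesises that these patients already have gut inflammation and impaired gut integrity, so a gut complaint could readily be put down to the underlying condition. An event that was not recorded cannot be recovered at analysis.

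At stake is the completeness of the safety comparison. No planned efficacy estimate or test is affected.

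**Working it through.** The documents state no event rate, safety threshold or safety power, so there is no figure to reproduce. The check compares the relevant sections.

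1. **Scope of the rule.** In III.C.7 the relation to probiotic intake qualifies which side effects are both assessed and reported. The grammar is imperfect. A looser reading, covering side effects that arise and may be related, still makes suspicion of a relation the entry condition. Only a reading that ignores the qualifier covers every event.

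2. **Where the filter falls.** Under III.A and III.C.6, staff do not know the arm and the tablets cannot be told apart. The relation can therefore only be judged against the study tablet, for patients in either arm. The condition would act on both arms, and events judged unrelated could be missing from both.

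3. **Whether section IV fills the gap.** It names a between-group comparison for laboratory parameters and descriptive reporting for the symptom index and food frequency. Its opening sentence, on analysing all data, names the software and defines no safety summary. No count of patients with side effects, by arm or overall, is listed.

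4. **Whether another instrument fills the gap.** III.C.6 says "Self administered HIV Symptoms Index questionnaire will be filled by the respondent on 0,4,8,12 weeks of intervention". This is unfiltered and covers both arms. Its stated purpose, under II.B.b, is "To determine the effect of Probiotic supplementation towards quality of life improvement". Nothing in the plan uses it to count patients with adverse or serious events.

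5. **Size.** The number of patients per arm is 80 / 2 = 40. The loss would depend on the true event rate and on the share of events judged related. The documents give neither, so no estimate is possible. One figure gives context: if every event were recorded and none of a given type occurred in one arm, the exact two-sided 95% upper limit for its rate would be 1 − 0.025^(1/40) = 0.088, or 8.8%. That limit reflects the size of the trial and does not measure the effect of the wording. It shows only that safety information is limited even with full recording.

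**The case against.** The strongest reply is that this is a wording problem. III.C.7 promises that side effects will be reported, does not say that other events are discarded, and is loose enough that its authors may have meant everything that arises. An event must also be noticed before its cause can be judged. This stands in part: the text does not prove that events would be lost. It does leave staff free to leave out events they think unrelated, and an explicit rule would remove that doubt.

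A reader might infer that all placebo-arm events are excluded because those patients take no probiotic. The documents do not support this. Blinded staff with indistinguishable tablets could not apply the condition to one arm only. Total loss of symptom information is also not credible, because the symptom index is completed in both arms at weeks 0, 4, 8 and 12.

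A reader might also infer that staff would have little basis for judging cause. Section I says "the direct benefits of probiotics supplementation for INR HIV patients have not been studied", which concerns benefits. The section does not discuss harms. The references include an earlier clinical trial of probiotics in treated HIV patients, whose safety content cannot be seen here. The exclusions for known Lactobacillus allergy and acute diarrhoea show some attention to tolerability. No conclusion on prior knowledge of harms can be drawn either way.

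Finally, the absence of a side-effect table from section IV would, taken alone, be no more than missing detail. It matters here because it accompanies a collection rule that may be incomplete.

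**Conclusion.** The point holds in limited form. As worded, III.C.7 makes assessment and reporting depend on a judged relation to probiotic intake. In this blinded design that would act on both arms and could take events judged unrelated out of the between-arm safety comparison. An even filter does not restore the missing events. Section IV does not provide for that comparison, and the symptom index is not planned as a substitute.

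The size of any loss cannot be estimated, and it may be nil if staff read the sentence broadly. The conclusion assumes that staff follow the sentence as written. It also assumes that the unavailable study-procedure figure holds no further safety provision; nothing in the text suggests that it does. This is an inexpensive improvement worth making. It is not a flaw that threatens the trial's main results.

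**What to change.** Reword III.C.7 so that all adverse events are recorded in both arms whatever their judged cause. Ask about them in the same way in both arms at the existing week 4, 8 and 12 questionnaire time points. Make relatedness to the study tablet and seriousness separate fields, completed by existing study staff while blinded, so that they describe an event and do not decide whether it is recorded.

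Add to section IV one descriptive table by randomised arm, giving the number and percent of patients with any adverse event and with any serious adverse event. No hypothesis test is needed; a risk difference with a 95% confidence interval is optional.

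The cost is a short extra form, a little staff time and one table. The protocol describes no clinician contact at weeks 4 and 8, so it should say which staff complete the two judgement fields. No new time points, laboratory tests or patients are needed.
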